0. Preparations:

A pre-trial email will be sent to the primary physicians on behalf of the district managements in order to inform about the trial. The text is provided in appendix No. 4. Feedback regarding receiving of the letter (full email boxes etc.) will be collected. Primary physicians would be able to choose to refrain from participating.

1. Finding the participants:

A. By using the Clalit health services computer system; an Excel table will be created; which will include these fields: Identity number; Name; Age; Sex; Clinic name; Primary physician name; Primary physician's email address; Nurse in charge at the clinic; email address of that nurse; Last BMI value of the last year; First BMI value of the previous year; Existence of a dietician visit on the last year; Last total cholesterol level; Whether dispensing of a cholesterol lowering medicine was recorded during the last 2 months; Name of (the last) cholesterol lowering medicine dispensed - with dose and quantity; Whether dispensing of a diabetes medicine was recorded during the last 2 months;

¹ AND as intersection

Name of (the last) diabetes medicine dispensed - with dose and quantity; Whether diagnosed with myocardial infarction; Whether diagnosed with brain infarction; Whether diagnosed with any cardiovascular disease.

B. Participants for each separate inclusion group, according to the criteria above, will be identified. At this stage, a new list will be created, where the people who don't fit any of the criteria will be excluded. Some of the participants may fit more than one criterion. Hence 7 subgroups are created:

- A) Patients that fit only alert 1. (Significant weight loss without dietitian assessment)
- B) Patients that fit only alert 2. (A potentially too tight medicinal diabetes treatment)
- C) Patients that fit only alert 3. (A potentially too tight medicinal cholesterol lowering)
- D) Patients that fit both alert 1. and alert 2.
- E) Patients that fit both alert 1. and alert 3.
- F) Patients that fit both alert 2. and alert 3.
- G) Patients that fit all alerts: 1. , 2. and 3.

C. Population size: According to 11.2014 there are about 5000 patients that fit these criteria at North district and a similar number at the South district, totaling ~ 10,000. This provides a sufficient statistical power to examine the effect on the main hypotheses. (We used Pearson χ^2 test, assuming a 3% to 1.8% decline in death rates, as observed in a similar setting).

2. Randomization:

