- a. Randomization aims to get an unbiased and equal division into an intervention group and a control group.
- b. Randomization will be via computer: by adding a column in the excel table, with the function =ROUND(RAND(),0). This means 1:1 randomization to 0 (control) or 1 (intervention letter).
- c. In order to avoid large differences in numbers of participants among the subgroups, the randomization procedure will repeat until the difference between control and intervention group is less than 2%.

3. The alert emails will be prepared and sent via "Mail Merge" (of Microsoft Word) to the primary physicians and to the nurses in charge at the same clinics. The templates to those emails are shown in the appendix. Technical problems (e.g. full mailbox of recipients) will be recorded and managed promptly (- days, hopefully), by the principal investigator.

4. Collecting outcome data: will be via the Clalit health services computer system. Data will include:

a. For all participants (control and trial groups), for the year that follows the intervention email:

1. Mortality (of any cause)
2. Days in stays (of any ward)
3. Number of stays
4. Number of physician visits
5. Number of nurse visits with symptoms
6. Number of all medicines dispensed
7. Medical expenses
8. Last BMI level and date
9. Last cholesterol level and date
10. Last HbA1c% level and date
11. Glucose levels of 70 mg/dL or less, and dates

b. For alert 1., for the year that follows the intervention email:

1. Recording of functional estimation by a nurse
2. Recording nutritional estimation by a nurse
3. Recording dietitian consultation

c. For alert 2. on the 3 months that follows the intervention email:

1. Whether a diabetes medicine was dispensed, and if so:
2. Name of diabetes medicine, dose and quantity

d. For alert 3. on the 3 months that follows the intervention email:

1. Whether a cholesterol lowering medicine was dispensed, and if so:
2. Name of medicine, dose and quantity

5. Data security: will be handled according to Clalit health systems procedures. The information will be saved in allowed secure servers only and will be available to authorized researchers only after their guidance and signing a non-disclosure commitment. When applicable, personal identification details will be omitted from the lists.

6. Outcome analysis:

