Categorical variables will be shown as frequencies and percentages. Continuous variables will be shown using standard distribution indices (e.g. average, standard deviation, median, etc.). Differences between the arms of the study will be examined using Chi-square test (or Fishers' exact test) for categorical variables and T-test (or Wilcoxon two sample test) for continuous variables. The statistical processing will be performed using Excel or SAS 9.2 software and will be statistically significant if $P < .05$.

7. Ethical issues of the trial:

A waiver of the requirement to obtain a signed informed consent from participants is requested with the following reason: There is no contact with the patients, only unsheathing their existing data.

A waiver of Form 11 is requested with the following reason:

The family physician will be the one who would get the alert related to this trial in the first place.

Appendixes:

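### Service use and costs are collected only for the year after the email and compared unadjusted, giving up precision that a prior-year value could supply

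*Combined protocol and SAP*

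**What the plan says.** Item 6 (Outcome analysis) is the whole analysis plan. For categorical outcomes it states: "Differences between the arms of the study will be examined using Chi-square test (or Fishers' exact test) for categorical variables". For continuous outcomes it names "T-test (or Wilcoxon two sample test) for continuous variables". It mentions no regression, covariate, change score or stratified test.

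Item 4 (Collecting outcome data), list a, covers all participants "for the year that follows the intervention email". Entries 2 to 7 are days in hospital, number of stays, physician visits, nurse visits with symptoms, the count of all dispensed medicines, and expenses. No period before the email is listed for any of them.

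Item 1 (Finding the participants) describes the baseline data: "an Excel table will be created; which will include these fields". Age and sex are among the fields, and the seven alert subgroups are formed from this table before randomisation. The table also holds the last diabetes or cholesterol-lowering medicine with dose and quantity, but no count of all medicines and no earlier stays, visits or expenses.

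The service-use and cost outcomes belong to hypothesis B (Other Study Hypotheses), not to the two main hypotheses.

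**The concern.** Use of care by people aged 75 and over is likely to differ widely between patients and to persist to some degree from one year to the next. If so, part of the between-patient variation in the year after the email could be predicted from the year before. A plain two-sample test leaves all of it in the error term.

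The earlier year is probably within reach. Baseline and outcome data come from the same computer system, and the participant table already looks back in time (an earlier BMI, dietician contact over the past year). That the system also holds prior-year stays, visits, medicines and expenses is a reasonable inference; the protocol does not state it.

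At stake is the precision of the hypothesis B comparisons: wider intervals and a greater chance of missing a modest effect on hospital use or cost.

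**Working it through.** **The plan's own figure.** The only sample-size statement concerns deaths: "assuming a 3% to 1.8% decline in death rates, as observed in a similar setting", with "a similar number at the South district, totaling ~ 10,000" patients, followed by "This provides a sufficient statistical power to examine the effect on the main hypotheses". No numerical power is given, so there is no figure to match. Taking 5,000 per arm, 3% v 1.8%, two-sided 0.05 (sidedness is not stated) and a pooled chi-square:

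- standard error under no difference: √(2 × 0.024 × 0.976 / 5,000) = 0.00306
- standard error under the alternative: √((0.03 × 0.97 + 0.018 × 0.982) / 5,000) = 0.00306
- power = Φ((0.012 − 1.96 × 0.00306) / 0.00306) = Φ(1.96) = 97.5%

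The pooled mortality comparison is therefore well powered at the plan's rates. The plan gives no corresponding calculation for service use or cost.

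**Gain for service use and cost.** Inputs: about 10,000 patients, 1:1 allocation (items 1 and 2), and r, the correlation between prior-year and follow-up values. The documents give no r, so a range of 0.2 to 0.6 is assumed.

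- Variance after adjustment, relative to unadjusted: 1 − r²
- Equivalent number of patients: 10,000 / (1 − r²)
- Power of a comparison that has 80% unadjusted: Φ(2.802 / √(1 − r²) − 1.960), where 2.802 = 1.960 + 0.842
- Difference detectable with 80% power at 5,000 per arm, in SD units: 2.802 × √(2 / 5,000) × √(1 − r²); unadjusted this is 0.056

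| Assumed r | Variance removed | 10,000 act like | 80% power becomes | Detectable difference (SD) |
|---|---|---|---|---|
| 0.2 | 4% | 10,417 | 82% | 0.055 |
| 0.3 | 9% | 10,989 | 84% | 0.053 |
| 0.4 | 16% | 11,905 | 86% | 0.051 |
| 0.5 | 25% | 13,333 | 90% | 0.049 |
| 0.6 | 36% | 15,625 | 94% | 0.045 |

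The r² rule applies to a linear comparison of means. It does not carry over to the Wilcoxon test, which the plan also allows. Any further gain from age, sex and alert subgroup is not counted.

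**Mortality, for comparison.** Logistic models were simulated at 3% v 1.8% and 10,000 patients, with and without age, sex and alert group, under three sets of assumed odds ratios. The efficiency ratio (adjusted z / unadjusted z)² was 1.011, 1.023 and 1.056. Power was 97.5% to 98.5% unadjusted and 97.5% to 99% adjusted, a difference within simulation error. A separate set of four assumed scenarios gave ratios of 1.006 to 1.085. Together these put the gain at roughly 1% to 9%.

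**The case against.** **The unadjusted tests are valid.** This stands. Omitting covariates from a randomised comparison brings no bias and no excess of false positives. Chance differences in prior illness are already reflected in the standard error. With 5,000 per arm, 95% of such differences in a prior-year measure fall within 1.96 × √(2 / 5,000) = 0.04 SD. The re-randomisation rule in item 2c limits differences in numbers of participants, not in prior illness, but that does not make the plain test wrong.

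**The size is unknown.** This also stands. A reader might infer that a large gain is being lost at no cost. The documents do not support that: they give no correlation, r may be low for stays and days in hospital, and at r = 0.2 the gain is only 4%. Nor is the gain without cost, since it needs another extraction.

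**Mortality.** A reader might infer that mortality suffers in the same way, from one chi-square pooled over very different patients. The documents do not say this. The main hypothesis on mortality is framed for each study group, and item 6 never says that the groups are pooled; it is silent on how they enter the analysis. Even in a pooled analysis the expected gain is small.

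**Only secondary outcomes are affected.** True. This limits the weight of the point, but the change is cheap and specific.

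**Conclusion.** The point holds as a loss of precision in the secondary service-use and cost outcomes. It is not a bias, and it does not bear materially on either main hypothesis. For a comparison of means, adjustment for the prior-year value would remove 4% to 36% of the variance if r lies between 0.2 and 0.6. A comparison with 80% power would then have about 82% to 94%.

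Two assumptions carry this: the range for r, which no document supplies, and the availability of prior-year data in the same system, which is likely but not stated. The absence of earlier values and of any adjustment in the written plan is plain from items 1, 4 and 6. This is a worthwhile, inexpensive improvement.

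**What to change.** 1. In item 4, add an extraction of entries a.2 to a.7 for the 12 months before the email, for every participant in both arms, with the same definitions as for the follow-up year.
2. In item 6, prespecify the main comparison of each measure as a regression on arm, the patient's prior-year value, age, sex and alert subgroup. Report the difference in means with a robust 95% confidence interval. A count model is an alternative for skewed counts. Fix the choice before outcome data are seen.
3. Keep the t-test or Wilcoxon test as a check.
4. For mortality, state how the alert groups enter the analysis. Any pooled comparison can be stratified by alert subgroup, mainly for clarity, since little precision is to be gained.

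The cost is one more database pull over an earlier date range and slightly more analysis. No patient contact is needed, and allocation and sample size do not change.

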BMI is a widely used as an index of nutritional problems. In a meta-analysis which included 2.88 million people, the optimal BMI for overall survival was found to be 25-30 kg/m² (Flegal, 2013; Dixon, 2014 ; Pan, 2012). Rapid weight loss is a strong indicator for health and functional decline. Such a weight loss, especially with low BMI values, usually mandates investigation in order to eliminate the cause or to limit its effect. A use of an automatic e-mail alert system was found to improve screening rate of malnourished patients in hospital (Giovannelli, 2014).

Correlation between death and HbA1c% is U-shaped, with increased mortality under a 6.5% level in patients taking two antidiabetic medicines (Currie, 2010). Among these patients, the optimal HbA1c% values of for survival were 7.5-8%. A substantial proportion of older adults with diabetes were found by Lipska et al. (2015) to be potentially overtreated.

Correlation between death and cholesterol is also U-shaped (Iso, 1989). Hypocholesterolemia is defined as cholesterol below 160 mg% and predicts increased mortality and morbidity (Hazzard's, p. 1341). We found no interventional study for this situation in the scientific literature.

In our experience, Email alerts to doctors, regarding an over-tight control of specified diabetic patients by sulphonyl-urea medicines was followed by a reduction (from 3% to 1.8%) in

mortality comparing to a previous-year matched control group (unpublished observations). While this result was not statistically significant, it encouraged us to try this large scale interventional clinical trial. It also served us in assessing the size of the study population needed.

Objectives:

This study aims to determine whether reminding physicians and nurses about too low values of weight (as BMI), glucose (as HbA1c%) or cholesterol (as total serum cholesterol) improves survival and health of people older than 75 years.

Study Hypotheses:

A. Main Study Hypotheses:

1. Compliance: Sending the intervention letter will cause a positive change in the relevant index (a rise in BMI, HbA1c%, or cholesterol, respectively).
2. Health effect: Sending the intervention letter will cause a lower mortality rate in each study group compared to control groups, within a year.

B. Other Study Hypotheses: compared to control groups, sending the intervention letter will cause improvement in morbidity and in secondary measures (see below).

And in detail:

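### Mortality is hypothesised in each study group, but the claim of sufficient power holds only for the pooled comparison, and no primary mortality test is named

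*Combined protocol and SAP*

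**What the plan says.** - **Hypothesis.** Study Hypotheses, A.2: "Sending the intervention letter will cause a lower mortality rate in each study group compared to control groups, within a year". It stands beside compliance (A.1) under the main hypotheses.
- **Power.** Section 1.C counts about 5,000 eligible patients in each of two districts, about 10,000 in all, and concludes: "This provides a sufficient statistical power to examine the effect on the main hypotheses". The basis is a Pearson chi-square test with deaths falling from 3% to 1.8%. No power figure and no size for any alert is given.
- **Source of the effect.** The background reports that e-mail alerts "regarding an over-tight control of specified diabetic patients by sulphonyl-urea medicines was followed by a reduction (from 3% to 1.8%) in" mortality, against matched patients of the year before. It adds that this was not statistically significant.
- **Groups.** Section 1.B: "Some of the participants may fit more than one criterion". It then defines seven exclusive subgroups, A to G.
- **Randomisation.** Section 2.a: "Randomization aims to get an unbiased and equal division into an intervention group and a control group".
- **Analysis.** Section 6: "Differences between the arms of the study will be examined using Chi-square test (or Fishers' exact test) for categorical variables", and results "will be statistically significant if $P < .05". It names no primary comparison, testing order or multiplicity adjustment, and does not say which mortality analysis a patient who fits several alerts enters.

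**The concern.** The hypothesis is stated per group, while the sizing and the randomisation are pooled. A claim of sufficient power for the main hypotheses should hold for the hypothesis as worded. Here it can be supported only for a comparison that A.2 does not describe.

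Section 6 also leaves the choice of mortality comparison open. Once outcomes are known, the pooled result or any single alert's result could be presented as the main finding at an unadjusted .05. The three letters ask clinicians for different things (Appendices 1 to 3), so a mortality benefit credited to one alert could be used to support one particular change in care. Such a claim would carry more than the nominal error and would rest on a comparison whose power was never stated.

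**Working it through.** **Inputs.** Deaths 3% and 1.8%, total about 10,000 (section 1.C); 1:1 allocation (section 2.b); .05 per test (section 6); three alerts (Methodology). Assumed: two-sided tests, because sidedness is not stated; the same effect in every alert; and all alert sizes, because none are given.

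**Step 1. The plan's own case (pooled).** With n per arm and p̄ = 0.024:

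power = Φ{ [p₁ − p₂ − z·√(2p̄(1 − p̄)/n)] / √[(p₁(1 − p₁) + p₂(1 − p₂))/n] }

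At n = 5,000 the two standard errors are 0.003061 and 0.003059. Then (0.012 − 1.96 × 0.003061)/0.003059 = 1.962, and Φ(1.962) = 97.5%. The plan prints no figure, but sufficient is a fair word for this comparison.

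**Step 2. One alert at a time.** Same formula:

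| Patients in the alert (assumed) | Power at .05 | Power at .0167 (Holm's first step) |
|---|---|---|
| 2,000 | 42% | 26% |
| 3,333 | 62% | 45% |
| 6,000 | 86% | 74% |

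80% power at .05 needs about 5,105 patients in the alert. Two such alerts need 2 × 5,105 = 10,210, more than the 10,000 available. With little or no overlap, at most one alert can therefore reach 80%. The smallest of three holds at most 10,000/3 = 3,333 patients, so its power is at most about 62%.

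*Effect of overlap.* Assume that 20% of patients fit several alerts, split 30:30:30:10 over subgroups D to G. Memberships are then 10,000 × (1 + 0.2 × 1.1) = 12,200, and the smallest alert holds at most 4,067 (about 71% power). At 50% overlap there are 15,500 memberships, so equal alerts of 5,167 would each just reach 80%. The bound thus depends on overlap being small.

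**Step 3. All three alerts must succeed.** There is no inflation of error. For equal, non-overlapping thirds, joint power is 0.619³ = 23.7%. For 2,000/2,000/6,000 it is 0.418² × 0.859 = 15.0%.

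**Step 4. Any one alert may be claimed.** For independent tests, 1 − 0.95³ = 14.3% two-sided, and 1 − 0.975³ = 7.3% for a false benefit. With the 20% to 50% overlap above, simulation gives 13% to 14% (6.6% to 7.0%). If the pooled test may be chosen as well, simulation gives about 16% (8%), for both equal thirds and a 2:2:6 split.

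**Step 5. If study group means subgroups A to G.** Any one of seven: 1 − 0.95⁷ = 30.2% (false benefit 1 − 0.975⁷ = 16.2%). The smallest of seven exclusive subgroups holds at most 10,000/7 ≈ 1,429 patients, fewer than the 2,000 that give 42%.

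**The case against.** **The error figures need a reading that the plan never states.** Read literally, a benefit in each group requires every group to succeed, which inflates nothing. This stands. A reader might infer that the trial runs at a 14% error rate; the documents do not support that, because no section says that one alert suffices. But the literal reading gives joint power of about 24% for equal thirds, which does not fit a claim of sufficient power.

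**The alerts may be three separate questions.** The letters label them LIMIT-A, LIMIT-B and LIMIT-C, each with its own criteria and index. Statisticians differ on whether to adjust across separate questions. That is a defensible position if declared in advance, but the plan does not declare it, and it would leave per-alert power unstated.

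**Mortality per group is already a main hypothesis, and no pooled mortality hypothesis is written.** True. The pooled reading comes from sections 1.C, 2 and 6. This shows the mismatch rather than resolving it.

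**Subgroups A to G handle patients with several alerts.** Only in part: they classify these patients, but section 6 does not use the classes.

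**Alert sizes are assumed.** Also true. The figures do not show that a given alert is underpowered, and with heavy overlap the bound in step 2 loosens. They show that the power claim cannot be carried from the pooled total to each group.

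**Conclusion.** The point holds as a mismatch between hypothesis, sizing and analysis. At 3% against 1.8% the pooled comparison has 97.5% power. With little overlap, at most one alert can reach 80%, and the smallest has at most about 62%. Requiring all three gives about 24% for equal thirds. Allowing any one gives up to about 14% family-wise error (7% false benefit), or about 16% (8%) with the pooled test added. Which of these applies cannot be settled from the documents.

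The per-alert figures assume the alert sizes and a common effect. That effect came from diabetic patients on sulphonyl-urea medicines, so extending it to the weight and cholesterol alerts is itself an assumption.

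A reader might go further and conclude that the trial is underpowered, or that its randomised comparison is unsound on this ground. Neither follows: the pooled comparison of arms is well powered at the assumed rates and needs no adjustment if named as the one primary test. The change should be made, because it decides which claim the trial can support.

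**What to change.** Write the following before outcome data are seen:

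1. **Primary (section 6).** One test: one-year all-cause mortality in all randomised patients, intervention against control, chi-square, two-sided .05. Reword A.2 to match.
2. **Secondary mortality (section 6).** Mortality per alert, counting each patient in every alert they fit, with 95% confidence intervals and Holm-adjusted P values over the three alerts. Make a confirmatory claim only if the primary test is significant; otherwise report as descriptive. This gate keeps error over all the mortality tests at 5%. Without it, the pooled test plus Holm gives about 8%.
3. **Compliance (section 6).** The three indices as a separate Holm family at .05, read as uptake of the alert and not as health benefit.
4. **Power (section 1.C).** Say that sufficient power refers to the pooled comparison only, and give per-alert power from the actual counts.

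If per-alert mortality is the intended main claim, use Holm over the three alerts without the pooled gate, and restate power per alert in 1.C.

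**Cost.** Text only, with no new data. There are three downsides:

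- A pooled primary can miss a benefit confined to one alert. If one of three equal groups benefits, pooled deaths are 3.0% against (1.8 + 3.0 + 3.0)/3 = 2.6%, and power is about 23%.
- Holm's first step lowers per-alert power, for example from 62% to 45% at 3,333 patients. 80% at that step needs about 6,810 in one alert.
- Separate mortality and compliance families leave up to .05 + .05 = about 10% across both main hypotheses.
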